9.3.2.3 Subject Retesting

Subjects who initially fail to qualify for the study based on laboratory test results may be retested once within the 8-week Screening period, per Investigator discretion (Section 7.4.1, Retesting).

9.3.3 Subject Rescreening

Subjects who fail to meet the qualifying criteria for Hb or eGFR during the Screening period may be considered for rescreening at the discretion of the Investigator if it is felt that the

subject's status has progressed and that the subject may now qualify for the study. Additionally, subjects who fail to qualify for the study based on low TSAT, ferritin, folate, or B₁₂ values may be considered for rescreening after receiving replacement therapy. Screening is limited to 3 attempts (Screening and 2 additional rescreening attempts) ([Section 7.4.2, Rescreening](#)).

9.3.4 Baseline Visit (Day 1)

[figure not shown]
The Baseline visit must be performed at a minimum of 4 days from the last Screening visit (SV2) procedure including retest(s).

At the Baseline visit, the following activities/procedures will be performed:

- Randomization
- 12-lead ECG (prior to vital sign assessments and blood draws).
- Vital signs including heart rate and blood pressure (assessed in seated position after 5 minutes of rest and prior to blood draws)
- Laboratory Procedures:
 - Random spot urine sample for uACR
 - Coagulation Tests
 - CRP
 - CBC (including differential)
 - Reticulocyte count
 - Serum chemistry including serum creatinine and eGFR
 - Liver function tests
 - Iron indices
 - Lipid profile
 - EPO
 - Biomarkers
 - PK (see [Section 9.2.2, Laboratory Evaluations](#); samples to be drawn only for subjects randomly assigned to vadadustat)
 - Exploratory samples
- Review of medical history for new conditions since Screening visit
- Medication use since Screening visit
- Study medication assessments and procedures:
 - Subject will take their first dose of study medication at the investigative site during the Baseline visit
 - Hb by HemoCue for dose initiation
 - Vadadustat dispensing
 - Darbepoetin alfa dispensing)
 - Oral iron supplementation as needed to maintain ferritin ≥ 100 ng/mL or TSAT $\geq 20\%$ (per local product label; see [Section 8.4.6, Iron Supplementation](#))
- AE assessment as needed (after receiving the first dose of study medication).
- Visit Registration in IWR

9.3.5 Year 1 Treatment Period Visits (Day 2 through Week 52)

During the Year 1 Treatment Period visits at Weeks 2, 4, 6, 8, 10, 12, 16, 20, 24, 28, 32, 36, 40, 44, 48, and 52, the following activities/procedures will be performed:

- Vital signs including heart rate and blood pressure (assessed in seated position after 5 minutes of rest and prior to blood draws)
- Weight (Weeks 12, 24, 36, and 52)
- Laboratory procedures:
 - Random spot urine sample for uACR (Weeks 28 and 52)
 - CBC (Weeks 2, 4, 6, 8, 10, 12, 16, 20, 24, 28, 32, 36, 40, 44, 48, and 52; differential at Weeks 28 and 52)
 - Reticulocyte count (Weeks 4, 12, 28, and 52)
 - Serum chemistry (Weeks 28 and 52)
 - Serum creatinine and eGFR (Weeks 4, 8, 12, 20, 36, and 44; also at Weeks 28 and 52 as part of the serum chemistry)
 - Liver function tests (Weeks 4, 8, 12, 16, 20, 24, 28, 36, 44, and 52)
 - Iron indices (Weeks 4, 8, 12, 20, 28, 36, 44, and 52)
 - Lipid profile (Weeks 28 and 52)
 - EPO (Weeks 4, 12, 28, and 52)
 - CRP (Weeks 28 and 52)
 - Biomarkers (Weeks 12, 28, and 52)
 - PK (Weeks 4, 12, 28, and 52; see [Section 9.2.2, Laboratory Evaluations](#); samples to be drawn only for subjects randomized to vadadustat)
 - Exploratory samples (Weeks 28 and 52)
- Record date and time of subject's last dose of vadadustat prior to the PK sample (Weeks 4, 12, 28, and 52)
- Safety assessments:
 - AE assessment
 - RBC transfusions and ESA rescue
 - Therapeutic phlebotomy
 - MACE endpoint questionnaire
- Medication assessments and procedures:
 - Review of concomitant medications
 - Hb by HemoCue for dose adjustment
 - Drug reconciliation: Study medication (vadadustat or darbepoetin alfa) reconciliation will be conducted per the pharmacy manual instructions.
 - Vadadustat dispensing as needed per [Section 8.2.1, Dispensing of Vadadustat](#)
 - Darbepoetin alfa dispensing
 - Iron supplementation as needed to maintain ferritin ≥ 100 ng/mL or TSAT $\geq 20\%$ (per local product label; see [Section 8.4.6, Iron Supplementation](#))
 - Question subject regarding dosing compliance and whether they have questions or have experienced any problems related to the dosing of study medication (vadadustat or darbepoetin alfa).
- Visit Registration in IWR

9.3.6 Year 2-4 Monthly Hb Monitoring

- Monthly monitoring of Hb as part of local standard of care labs or at unscheduled visits for dose adjustment.

9.3.7 Year 2 Treatment Period Visits (Weeks 53 through 104)

[figure not shown]
During the Year 2 Treatment Period visits at Weeks 64, 76, 88, and 104, the following activities/procedures will be performed:

- Vital signs including heart rate and blood pressure (assessed in seated position after 5 minutes of rest and prior to blood draws)
- Weight (Week 104)
- Laboratory Procedures:
 - Random spot urine sample for uACR (Week 104)
 - CBC (Weeks 64, 76, 88, and 104; differential at Weeks 76 and 104)
 - Serum chemistry including serum creatinine and eGFR (Weeks 76 and 104)
 - Liver function tests (Weeks 64, 76, 88, and 104)
 - Iron indices (Weeks 64, 76, 88, and 104)
 - CRP (Week 104)
 - Biomarkers (Week 104)
 - Exploratory samples (Week 104)
- Safety assessments:
 - AE assessment
 - RBC transfusions and ESA rescue
 - Therapeutic phlebotomy
 - MACE endpoint questionnaire
- Medication assessments and procedures:
 - Review of concomitant medications
 - Hb by HemoCue for dose adjustment
 - Drug reconciliation: Study medication (vadadustat or darbepoetin alfa) reconciliation will be conducted per the pharmacy manual instructions.
 - Vadadustat dispensing as needed per [Section 8.2.1, Dispensing of Vadadustat](#)
 - Darbepoetin alfa dispensing
 - Iron supplementation to maintain ferritin ≥ 100 ng/mL or TSAT $\geq 20\%$ (per local product label; see [Section 8.4.6, Iron Supplementation](#))
 - Question subject regarding dosing compliance and whether they have questions or have experienced any problems related to the dosing of study medication (vadadustat or darbepoetin alfa).
- Visit Registration in IWR

9.3.8 Year 3/4 Treatment Period Visits (Weeks 116 through 208)

During the Year 3/4 Treatment Period visits at Weeks 116, 128, 140, 156, 168, 180, 192, and 208, the following activities/procedures will be performed:

- Vital signs including heart rate and blood pressure (assessed in seated position after 5 minutes of rest and prior to blood draws)
- Weight (Weeks 156 and 208)
- Laboratory Procedures:
 - Random spot urine sample for uACR (Weeks 156 and 208)
 - CBC (Weeks 116, 128, 140, 156, 168, 180, 192, and 208; differential at Weeks 128, 156, 180, and 208)

[figure not shown]
- Serum chemistry including serum creatinine and eGFR (Weeks 128, 156, 180, and 208)
- Liver function tests (Weeks 116, 128, 140, 156, 168, 180, 192, and 208)
- Iron indices (Weeks 116, 128, 140, 156, 168, 180, 192, and 208)
- CRP (Week 156)
- Biomarkers (Week 156)
- Exploratory samples (Week 156)
- Safety assessments:
 - AE assessment
 - RBC transfusions and ESA rescue
 - Therapeutic phlebotomy
 - MACE endpoint questionnaire
- Medication assessments and procedures:
 - Review of concomitant medications
 - Hb by HemoCue for dose adjustment
 - Drug reconciliation: Study medication (vadadustat or darbepoetin alfa) reconciliation will be conducted per the pharmacy manual instructions.
 - Vadadustat dispensing as needed per [Section 8.2.1, Dispensing of Vadadustat](#)
 - Darbepoetin alfa dispensing (per PI for investigational sites in the US, and the SmPC for all other investigational sites (non-US))
 - Iron supplementation to maintain ferritin ≥ 100 ng/mL or TSAT $\geq 20\%$ (per local product label; see [Section 8.4.6, Iron Supplementation](#))
 - Question subject regarding dosing compliance and whether they have questions or have experienced any problems related to the dosing of study medication (vadadustat or darbepoetin alfa).
- Visit Registration in IWR

9.3.9 End of Treatment (EOT) Visit

The EOT visit will be performed at the time a subject permanently discontinues study medication or for subjects on study medication at the time of notification of global study completion (See [Appendix A: Schedule of Activities](#)).

At the EOT visit, the following activities/procedures will be performed:

- Vital signs including heart rate and blood pressure (assessed in seated position after 5 minutes of rest and prior to blood draws), as well as weight
- Laboratory Procedures:
 - Random spot urine sample for uACR
 - CBC (without differential)
 - Serum chemistry including serum creatinine and eGFR
 - Liver function tests
 - Iron indices
 - Biomarkers
 - CRP
 - Exploratory samples
- Safety assessments:
 - AE assessment

- RBC transfusions and ESA rescue
- Therapeutic phlebotomy
- MACE endpoint questionnaire
- Recording of concomitant medications
- Drug reconciliation: Study medication (vadadustat or darbepoetin alfa) reconciliation will be conducted per the pharmacy manual instructions.
- Question subject regarding dosing compliance and whether they have experienced any problems related to the dosing of study medication (vadadustat or darbepoetin alfa).
- Visit Registration in IWR

9.3.10 Follow-Up Visit

The Follow-up visit will be conducted in person or via the telephone 4 weeks after the EOT visit. The following activities/procedures will be performed:

- AE assessment
- RBC transfusions and ESA rescue
- Therapeutic phlebotomy
- MACE endpoint questionnaire.
- Recording of concomitant medications

9.3.11 Unscheduled Visits

Unscheduled assessments may be conducted at any time as medically warranted. The following activities/procedures will be performed. At a minimum,

- MACE Endpoint Questionnaire
- AE assessments
- Any other procedures that are medically warranted at the discretion of the Investigator

9.3.12 End of Study Subject Status

The End of Study (EOS) assessment documents the subject status at the global study completion or at the time of subject withdrawal of consent or when subject is deemed LTFU or upon death. The table below outlines how to handle each subject based on their status.

The following activities/procedures will be performed. At minimum,

- EOS subject status

Subject Status	Global Study Completion
Subject on Study Medication (includes those on temporary interruption) at time of global study completion	
● Perform EOT visit● Perform the Follow-up visit 4 weeks after EOT and include EOS subject status

Subject permanently discontinued study medication and continues to be followed in the study	Optimal data collection would include the following assessments: 
 • EOS subject status (must collect at minimum) • MACE Endpoint Questionnaire • AE Assessment NOTE: EOT and the Follow-up visit 4 weeks after EOT visit to be performed at time study medication is permanently discontinued.
Subject Lost to Follow-up	Work with third party vendor to ascertain vital status and complete EOS subject status. If subject-site contact is reestablished and possible, collect available information for EOS subject status.
Subject Withdrawn Consent	Complete the EOS subject status form at the time of withdrawal of consent, absolute refusal of ALL methods of MACE and health status follow-up.
Subject Death	Complete the EOS subject status form at the time of death (see Section 10 Adverse Events for more details on other actions related to reporting a death).

9.4 Study Medication Stopping Rules

Study medication must be permanently discontinued if a subject meets one of the criteria in Table 2 below

Table 2. Study Medication Stopping Rules

ALT or AST >3x ULN and total bilirubin >2x ULN	Permanently Discontinue Treatment
ALT or AST >3x ULN and INR >1.5	Permanently Discontinue Treatment
ALT or AST >8x ULN	Permanently Discontinue Treatment
ALT or AST remains >5x ULN over 2 weeks*	Permanently Discontinue Treatment
ALT or AST >3x ULN with symptoms including e.g., fatigue, nausea, vomiting, right upper quadrant pain, fever, rash or eosinophilia	Permanently Discontinue Treatment

* Re-challenge generally should be avoided with ALT or AST >5 times ULN unless there are no other good therapeutic options.

ALT: alanine transferase; AST: asparagine transferase; INR: international normalized ratio; ULN: upper limit of normal

See Section 10.1.1, Adverse Events for reporting requirements related to a subject being permanently discontinued based on meeting the laboratory abnormalities list above in [Table 2](#).

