

Phlebotomy
	
If a subject's Hb exceeds 14.0 g/dL or the rate of rise of Hb raises concern to the Investigator, the subject may be phlebotomized based on the Investigator's judgment. The method of phlebotomy will be in accordance with the investigative site's standard clinical practice.

Study Medication Stopping Rules
	
Study medication must be permanently discontinued if a subject meets one of the criteria.
 
 • ALT or AST >3x Upper Limit of Normal (ULN) and total bilirubin >2x ULN • ALT or AST >3x ULN and INR >1.5 • ALT or AST >8x ULN • ALT or AST remains >5x ULN over 2 weeks* • ALT or AST >3x ULN with symptoms (e.g., fatigue, nausea, vomiting, right upper quadrant pain, fever, rash) or eosinophilia 
*Re-challenge generally should be avoided with ALT or AST >5x ULN unless there are no other good therapeutic options.

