Refer to [Sections 7.4.1, Retesting](#) and [7.4.2, Rescreening](#) for further details regarding repeating laboratory measurements during the Screening period.

- **Point of care Hb:** Using HemoCue, Hb will be monitored throughout the study to determine if the dose of study medication (vadadustat or darbepoetin alfa) will be

adjusted, interrupted, or maintained as described in [Section 8.4.4 Dosing and Dose Adjustment Guidelines](#).

- Reticulocyte count: An automated reticulocyte count (both absolute and percent) will be performed at Baseline and at Weeks 4, 12, 28, and 52.
- Coagulation tests: Blood samples will be drawn at Baseline to assess the prothrombin time (PT), partial thromboplastin time (PTT), and international normalized ratio (INR).
- Folate and Vitamin B₁₂: A blood sample will be drawn at SV1 to assess the folate and Vitamin B₁₂ levels.
- Urine albumin-to-creatinine ratio (uACR): A random urine spot sample should be collected at the investigative site during the Baseline, Weeks 28, 52, 104, 156, 208, and EOT to assess the uACR. Subjects should refrain from heavy exercise 24 hours before the test.
- C-reactive protein (CRP): A blood sample for CRP will be collected at the Baseline, Weeks 28, 52, 104, 156, and EOT.
- Serum Chemistry: Blood samples to assess serum chemistry will be collected at SV1, Baseline, and twice annually at Weeks 28, 52, 76, 104, 128, 156, 180, 208, EOT. At all other noted visits in [Appendix A: Schedule of Activities](#), serum creatinine and eGFR will be performed only at Weeks 4, 8, 12, 20, 36, 44. The serum chemistry will include the following assays: sodium, potassium, bicarbonate, chloride, calcium, magnesium, phosphorus, glucose, creatinine, blood urea nitrogen (BUN), creatine phosphokinase (CPK), uric acid, albumin, total protein, and eGFR calculation.
Note: When a $\geq 50\%$ decline in eGFR from the Baseline value is observed, a repeat central laboratory measure should be performed within 30 to 60 days.
- Liver Function Tests: Blood samples to assess liver function will be collected at SV1, Baseline, Weeks 4, 8, 12, 16, 20, 24, 28, 36, 44, 52, 64, 76, 88, 104, 116, 128, 140, 156, 168, 180, 192, 208, and EOT. Liver function tests will include: total bilirubin, alkaline phosphatase, ALT/SGPT, AST/SGOT, and lactate dehydrogenase (LDH).

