If new elevations in ALT or AST > 3 times ULN, **without** an elevation of total serum bilirubin >2 times ULN are identified, the following steps are to be taken:

- Temporary discontinuation of Investigational Medicinal Product (IMP);
- Repeat testing of ALT, AST, ALP, and total bilirubin, should be completed within 48 to 72 hours to confirm the abnormalities and to determine trend;
- IMP should not be resumed until monitoring indicates abnormalities have resolved or have stabilized.

Details on the management of subjects with other ALT and AST abnormalities are further described in [Section 9.4, Study Medication Stopping Rules](#).

Worsening of Anemia – In this study, it is possible that some subjects may experience a worsening of anemia. As the primary endpoint of this study assesses Hb response, worsening of anemia is captured as part of this efficacy parameter. Worsening of anemia should not be considered an AE unless the worsening of anemia is associated with a cause *other than* the subject's CKD.

Transplantation – During this long-term study, it is anticipated that some subjects may receive a kidney transplant. These events will not be recorded as AEs. Subjects will discontinue study medication for receipt of a kidney, other solid organ, hematopoietic stem cell or bone marrow transplant and should continue with the Schedule of Activities and safety assessments as described in [Section 7.5.5.2, Permanent Discontinuation of Study Medication](#).

Malignancy – During this long-term study, some subjects may develop a newly diagnosed malignancy or a recurrence of a malignancy. At the discretion of the Investigator, these subjects may continue study medication (vadadustat or darbepoetin alfa). For reporting of adverse events of malignancy, see [Section 10.1.2 Serious Adverse Events](#).

Renal-Related Events - Some subjects will experience a progression of their CKD over the course of this study as part of the natural course of the disease. In addition, the study population is prone to experience acute, transient loss of kidney function of different etiologies, sometimes concomitantly complicated by progression of CKD.

To ensure consistent reporting of renal events, the following guidelines are to be used when reporting a renal-related AE:

- The following situations **should always be reported as SAEs** with seriousness criterion “medically important,” if no other seriousness criteria are met (see Section 10.1.2, Serious Adverse Events):

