- [l] Coagulation tests: prothrombin time (PT), partial thromboplastin time (PTT), and international normalized ratio (INR).
- [m] A CBC with differential will be performed at Baseline and twice annually at Weeks 28, 52, 76, 104, 128, 156, 180, 208. At all other noted visits, a CBC without differential will be performed.

- CBC: hemoglobin, hematocrit, red blood cells (RBC), mean corpuscular volume (MCV), mean corpuscular hemoglobin (MCH), mean corpuscular hemoglobin concentration (MCHC), red cell distribution width (RDW), white blood cell (WBC) count with differential (neutrophils, lymphocytes, monocytes, eosinophils, basophils), and platelets.
- [n] Mean Screening Hb between 8.0 and 11.0 g/dL (inclusive) in the US and between 9.0 and 12.0 g/dL (inclusive) outside of the US, as determined by the average of 2 Hb values measured by the central laboratory during Screening. If the subject's Hb does not qualify after SV1, SV2, or retest, the subject should be considered a Screen Failure.
 - [o] Iron indices: ferritin, iron, total iron binding capacity (TIBC), and transferrin saturation (TSAT).
 - [p] A full serum chemistry panel will be performed at SV1, Baseline, and twice annually at Weeks 28, 52, 76, 104, 128, 156, 180, 208. At all other noted visits, serum creatinine and eGFR will be performed. Serum chemistry: sodium, potassium, bicarbonate, chloride, calcium, magnesium, phosphorus, glucose, creatinine, blood urea nitrogen (BUN)/urea, creatine phosphokinase (CPK), uric acid, albumin, total protein, and eGFR.
 - [q] Liver function tests: total bilirubin, alkaline phosphatase, alanine aminotransferase (ALT/SGPT), aspartate aminotransferase (AST/SGOT), and lactate dehydrogenase (LDH).
 - [r] Lipids: total cholesterol, low density lipoprotein (LDL), high density lipoprotein (HDL), and triglycerides.
 - [s] The biomarkers include, but are not limited to, hepcidin and VEGF.
 - [t] PK samples are to be drawn only for subjects randomized to vadadustat. Subjects will be questioned regarding the timing of their last dose of vadadustat.
 - [u] Additional blood and urine samples will be collected at Baseline, Weeks 28, 52, 104, 156, and EOT which may be used for exploratory measurement of biomarkers (eg, factors relating to the activation of the HIF pathway). Subjects will also be asked to provide optional consent to obtain a blood sample at Baseline and EOT to be stored for future genetic analyses (eg, DNA, mRNA).

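### Amendment 7-COL: the liver stopping rule on INR >1.5 cannot be judged from any test the protocol requires after Baseline

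*Protocol*

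**What the plan says.** All references are to the Amendment 7-COL text of the protocol.

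- **The rule.** Section 9.4, Table 2, lists five criteria. Meeting any one of them makes permanent discontinuation of study medication obligatory. Row 2 is "ALT or AST >3x ULN and INR >1.5". The synopsis words the fifth criterion as "ALT or AST >3x ULN with symptoms (e.g., fatigue, nausea, vomiting, right upper quadrant pain, fever, rash) or eosinophilia".
- **INR.** Section 9.2.2: "Blood samples will be drawn at Baseline to assess the prothrombin time (PT), partial thromboplastin time (PTT), and international normalized ratio (INR"). Coagulation tests are in the Baseline list (Section 9.3.4) and have a single Baseline mark in the Appendix A grid. They appear in no later visit list.
- **Liver panel.** Section 9.2.2: "Liver function tests will include: total bilirubin, alkaline phosphatase, ALT/SGPT, AST/SGOT, and lactate dehydrogenase (LDH").
- **Work-up when ALT or AST exceeds 3x ULN without bilirubin above 2x ULN.** Section 10.1.1 puts study drug on temporary hold and adds: "Repeat testing of ALT, AST, ALP, and total bilirubin, should be completed within 48 to 72 hours". Drug may not restart before monitoring shows that the abnormalities have gone or settled. The same section then refers to 9.4 for other ALT and AST abnormalities.
- **Reporting.** New elevations above 3x ULN go to the Medical Monitor or CRO designee as an SAE within 24 hours. The change table for 10.1.1 shows the second condition, that no other cause has been found.
- **Anything further.** Section 9.3.11 leaves other procedures at unscheduled visits to the investigator.

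**The concern.** A compulsory stopping rule needs a measurement that someone is obliged to make. Row 2 protects subjects whom the other rows miss: transaminases above 3x ULN, bilirubin not above 2x ULN, but impaired clotting. Section 10.1.1 sends exactly these subjects to a temporary hold, followed by a repeat panel with no INR in it.

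If nobody orders the test, the subject looks like an ordinary hold. Restart can then be considered once the enzymes have settled, although Table 2 would have required a permanent stop. Amendment 7-COL was issued on guidance about drug-induced liver injury and revised the 10.1.1 text around the repeat panel, yet it added no INR there.

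The stake is patient safety. The primary efficacy and MACE results are not in question.

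**Working it through.** There is no plan figure to reproduce. The check sets what each Table 2 row needs against what the protocol requires to be measured.

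**Step 1. Rows against the 48 to 72 hour repeat panel (ALT, AST, ALP, total bilirubin).**

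| Table 2 row | Needed besides ALT/AST | In the repeat panel? |
|---|---|---|
| 1. >3x ULN and bilirubin >2x ULN | Total bilirubin | Yes |
| 2. >3x ULN and INR >1.5 | INR | No |
| 3. >8x ULN | Nothing | Yes |
| 4. Stays >5x ULN over 2 weeks | Serial values | Yes, with further draws |
| 5. >3x ULN with symptoms or eosinophilia | Symptoms, or an eosinophil count | Count: no. Symptoms: obtainable by questioning |

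**Step 2. Scheduled tests (Section 9.2.2 and Appendix A).**

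- Post-baseline liver tests: Weeks 4, 8, 12, 16, 20, 24, 28, 36, 44 and 52 (10 visits); 64, 76, 88 and 104 (4); 116, 128, 140, 156, 168, 180, 192 and 208 (8). Total 10 + 4 + 8 = 22, plus EOT.
- INR at those visits: 0 of 22.
- CBC with differential: Weeks 28, 52, 76, 104, 128, 156, 180 and 208, all of them liver-test visits. That is 8 of 22 (2 of 10 in Year 1), leaving 22 − 8 = 14 without an eosinophil count.

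**Step 3. Reading the two together.** Row 2 is the only row that no required measurement can settle. A Baseline INR says nothing about clotting at the time of a later transaminase rise. Row 5 differs: a count exists at some visits, and symptoms alone satisfy the row. AE assessment is a minimum item at unscheduled visits (9.3.11), and subjects are asked about AEs at every visit (10.2).

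**Step 4. Who is left exposed.** The subject must have ALT or AST above 3x ULN, bilirubin not above 2x ULN, values that meet neither row 3 nor row 4, nothing that meets row 5, and an INR above 1.5 that nobody measured. The documents give no frequency for this combination.

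**The case against.** The strongest reply is that little harm can follow. Drug is already on hold above 3x ULN. Unexplained cases reach the Medical Monitor or CRO designee within 24 hours, and looking for another cause implies some work-up. A rule that names INR also prompts a careful investigator to order one. All of this stands, and it narrows the risk to the restart decision. It does not supply the INR: neither the hold nor the SAE report calls for one, and Section 10.1.1 names its repeat analytes without it.

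A second reply is that a compulsory INR brings its own problem. Section 7.3 does not exclude anticoagulant users, and the amendment history in Appendix F says that long-term anticoagulation for an older DVT or PE is not exclusionary. Against an absolute cut-off of 1.5, such subjects could be stopped permanently because of the anticoagulant. This is right, and the fix has to deal with it.

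Three stronger readings are tempting but not supported:

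- **That eosinophilia is as unmonitored as INR.** It is not: 8 of 22 visits against 0 of 22. The synopsis separates eosinophilia from symptoms, but Table 2 itself lists it among them, and either way symptoms suffice.
- **That 10.1.1 contradicts 9.4 on resumption.** The restart wording is a minimum condition. Section 9.4 is obligatory, and 10.1.1 and 7.5.5 both point to it.
- **That the EOT visit shows the same gap.** It has no coagulation test and its CBC lacks a differential. For an early stop, however, that visit follows the decision to discontinue, so it cannot affect whether the trigger is recognised.

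**Conclusion.** The concern holds for INR. Followed as written, row 2 of Table 2 depends on a test that the protocol does not require after Baseline, so it can operate only through investigator discretion. The eosinophil gap is real but secondary.

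The remaining risk is narrow: resumption after a hold in a subject with an unmeasured INR above 1.5 who meets no other row. Its frequency cannot be estimated from the documents. This is worth fixing because the rule concerns safety and the remedy is cheap, not because any trial result is threatened.

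Two limits apply. The gap is shown only for the Colombia-specific text, and a reader should not extend it to other versions of the protocol. It also assumes that no document outside this set, such as a laboratory manual, already adds a reflex INR.

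**What to change.** 1. In Section 10.1.1, add INR to the 48 to 72 hour repeat whenever ALT or AST exceeds 3x ULN. Add a CBC with differential as a secondary item.
2. In Section 9.4, Table 2, row 2 (and the matching synopsis line), state that for subjects on anticoagulants the INR is judged against their Baseline or therapeutic INR, not the absolute 1.5 cut-off. This has to be in the rule itself: otherwise the compulsory wording overrides any baseline-relative reading.

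No extra sentence on resumption is needed, given the obligation in 9.4 and the existing pointers to it.

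The cost is amendment text plus one or two assays on a draw that 10.1.1 already requires, and only in subjects with ALT or AST above 3x ULN. Visits, sample size and analyses do not change.
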